Continuous data will be expressed as means \pm standard-deviations. Independent and dependent t-test with two-tail distribution will be performed to compare variables between and within the two groups, when a normality assumption holds according to Kolmogorov-Smirnov test. Categorical data will be expressed in numbers and percentages and compared by chi-square tests. Univariate analyses were performed using Chi-Square/Fisher's exact test to identify significant variables. A value of $p<0.05$ will be considered significant.

Data analysis will be performed with Matlab R2019b (Mathworks, Natick, MA) Statistics Toolbox.

Sample Size: 30

Based on a previous study on HBOT effect on ARDS [14], with 95% power and significance level of 5%, and a groups difference of 30 (SD 15-18) in the PaO₂/FiO₂ and a 2:1 groups allocation, the sample requires 7 NBOT patients and 13 HBOT patients. Considering 15% dropout, we will recruit 10 NBOT patients and 20 HBOT patients, 30 in total.

Expected Outcomes:

The primary outcomes measures that will be accessed in the study are:

- Oxygenation index = PaO₂/FiO₂ one day after the last session.
- SpO₂ – room air saturation one hour before and after a session, 6 hours after a session and one day after the last session.
- NES – Early warning score, before and after each session, 6 hours after each session and one day after the last session
- Inflammatory parameters one day after the last session: WBC, Immune profile, CRP, ESR, Procalcitonin, TNF α , IL1, IL2, IL6, IL10.

The secondary outcomes measures that will be accessed in the study are:

- Oxygenation index = PaO₂/FiO₂ one week after the last session.
- SpO₂ – room air saturation one week after the last session.
- NES – Early warning score, one week after the last session
- Inflammatory parameters one week after the last session: WBC, Immune profile, CRP, ESR, Procalcitonin, TNF α , IL1, IL2, IL6, IL10.
- Symptoms level one day and one week after the last session
- Viral load one day and one week after the last session
- Chest Xray changes one day and one week after the last session
- Percentage of patients with positive IgG serology one day and one week after the last session
- Percentage of patients with positive IgM serology one day and one week after the last session
- Pulmonary function test one day and one week after the last session
- Time to symptoms recovery
- Percentage of patients who required invasive intubation
- Time to recovery (negative PCR twice) – TT_{CR}

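### If symptom level or chest X-ray change is recorded in ordered grades, the plan offers only tests that ignore the order

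*Combined protocol and SAP*

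**What the plan says.** All references are to the combined protocol and SAP.

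- **Outcomes.** Study Objectives and Expected Outcomes both list "Symptoms level one day and one week after the last session" and "Chest Xray changes one day and one week after the last session" as secondary. Neither place gives a scale, a number of grades, a scoring rule or a data type.
- **Collection.** Data Collection Procedures has a symptoms questionnaire at baseline, on each of days 2 to 4, and at both follow-up visits. Its assessment lists contain no chest X-ray.
- **Continuous data.** Data Analysis states: "Independent and dependent t-test with two-tail distribution will be performed to compare variables between and within the two groups", but only "when a normality assumption holds according to Kolmogorov-Smirnov test". It names no test for data that fail this check.
- **Categorical data.** "Categorical data will be expressed in numbers and percentages and compared by chi-square tests". A further sentence adds Fisher's exact test: "Univariate analyses were performed using Chi-Square/Fisher's exact test to identify significant variables".
- **Not named.** There is no rank test, trend test or proportional-odds model. Neither of the two outcomes is assigned to a test by name.

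**The concern.** The outcome list words its yes/no outcomes as percentages of patients (positive serology, intubation). Symptom level and X-ray change are not worded that way, and both terms suggest degree or direction. If they are recorded in grades and summarised as counts and percentages, the categorical rule sends them to chi-square or Fisher's exact test.

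On a table of two arms by k grades, both tests give the same result however the grades are arranged. They divide their sensitivity among all possible patterns, including patterns that favour neither arm. With 10 NBOT patients spread evenly, the expected count per NBOT cell is 10/3 = 3.3 with 3 grades and 10/5 = 2 with 5. Fisher's exact test deals with small counts but does not restore the order.

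The numeric route does not fully close the gap. A symptom score that fails the normality check has no test in the plan. Left open, the choice among t-test, chi-square and merged grades could be made after the data are seen.

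**Working it through.** **1. The plan's own figure.** The only power statement concerns PaO₂/FiO₂: "with 95% power and significance level of 5"%, difference 30, SD 15–18, 2:1 allocation, giving 7 NBOT and 13 HBOT. The tests are two-sided ("t-test with two-tail distribution").

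Normal approximation: n(NBOT) = (1 + 1/2) × (1.960 + 1.645)² × SD² / 30² = 0.02166 × SD², and n(HBOT) is twice the rounded-up NBOT number.

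| SD | 0.02166 × SD² | NBOT + HBOT | t-test power at 7 + 13 |
|---|---|---|---|
| 15 | 4.87 | 5 + 10 | 98.1% |
| 16.5 | 5.90 | 6 + 12 | 95.6% |
| 18 | 7.02 | 8 + 16 | 91.9% |

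The last column uses the noncentral t distribution with 18 degrees of freedom and noncentrality 30 / (SD × √(1/7 + 1/13)). The stated 7 + 13 is reproduced at a mid-range SD. It says nothing about power for symptom level or X-ray change.

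**2. Inputs for the graded case.**
- From the plan: 10 NBOT v 20 HBOT, two-sided 5%. After 15% dropout, 0.85 × 20 = 17 and 0.85 × 10 = 8.5, taken as 8.
- Assumed, because the plan gives none of it: the number of grades (3, 4, 5 or 7), how patients spread over them, and a proportional shift, logit P(grade ≤ j) in HBOT = logit P(grade ≤ j) in NBOT − log(OR), with OR from 2 to 15.

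**3. Tests compared**, 20,000 simulated trials per setting.
- Pearson chi-square: Σ(O − E)²/E, with degrees of freedom equal to the number of non-empty grades minus 1.
- Wilcoxon rank-sum: z = (W − n₁(N+1)/2)/√V, with V = (n₁n₂/12) × [(N+1) − Σ(t³ − t)/(N(N−1))], where t is the number of patients tied in each grade.

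**4. Power gained by the rank test, in percentage points, OR 2–15.**

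| Grades | 10 v 20 | 8 v 17 |
|---|---|---|
| 2 (yes/no) | 0 | 0 |
| 3 | 2 to 9 | 1 to 8 |
| 4 | 5 to 17 | 3 to 17 |
| 5 | 7 to 22 | 5 to 22 |
| 7 | 9 to 27 | 8 to 25 |

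A separate run at 10 v 20 with equally likely grades and OR 2–6 gave about 2–7, 4–14 and 6–19 points for 3, 4 and 5 grades. Taken together, the 5-grade range is about 6 to 22.

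**5. Examples at OR 5, 10 v 20 (chi-square v Wilcoxon).**
- 3 equal grades: 50% v 56%.
- 4 equal grades: 45% v 60%.
- 5 grades at 0.1/0.2/0.4/0.2/0.1: 38% v 60%.

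**6. Is it the order, or this particular test?** At 8 v 17, with the same 5 grades and OR 5, power is 30.6% for chi-square, 50.9% for Wilcoxon and 51.9% for a trend test. Either test that uses the order recovers the loss.

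**7. No effect.** Wilcoxon rejected in 4.8–5.1% of trials and chi-square in 3.2–5.2%.

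**The case against.** The strongest reply is that the premise is not in the documents. They name these outcomes but do not say that they are graded. X-ray change could be yes/no, with no order to lose. The questionnaire could give a numeric score that goes to the t-test. The adverse event section also points to a research protocol of an overall study, which is not available here and may define the scales. This stands, and it is why the point is conditional. A reader might infer that both outcomes are graded and assigned to chi-square alone; the documents do not support that.

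A reader might also take a loss of about 20 points as the general size. It needs about 5 or more assumed grades and a large effect. For a reading of better, same or worse, the loss is at most about 9 points.

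Three further objections stand in part:
- **The simulation suits the rank test.** A proportional shift is the kind of difference that rank tests detect well. With many sparse grades, part of the gap also comes from a conservative chi-square. That is still a cost of the planned test, but not all of the gap is lost ordering.
- **Direction.** It would be too strong to say that a significant chi-square leaves the better arm unknown. The plan reports percentages by arm, so direction can often be read from them. But the test itself does not address direction, and with several grades the percentages may not point one way.
- **Data already in hand.** This holds for symptoms. It cannot be assumed for X-ray, which is absent from the assessment lists.

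**Conclusion.** The point holds conditionally. It is certain from the text that no planned method uses order, that neither outcome has a stated scale, and that a score failing the normality check has no named test. It is assumed that at least one of the outcomes is recorded in ordered grades.

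On that assumption, and under a proportional shift with OR 2–15, the cost at 20 v 10 is about 2–9 points of power for 3 grades and about 6–22 for 5. After 15% dropout it is slightly less. For a yes/no outcome it is zero. The direction was the same in every range obtained for 3 or more grades; only the size depends on the scale.

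The consequence is limited. Both outcomes are secondary and were not used to set the sample size, and the PaO₂/FiO₂ calculation is untouched. This is a low-cost improvement and not a threat to the trial's main result.

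**What to change.** In Data Analysis:

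1. State the scale of symptom level and of chest X-ray change: numeric score, ordered grades (and how many), or yes/no.
2. Where the scale is ordered, including a symptom score that fails the normality check, compare arms at each time point with the tie-corrected or exact Wilcoxon rank-sum test. Report the probability that an HBOT patient does better than an NBOT patient, state how ties count, and give its 95% confidence interval.
3. Keep chi-square or Fisher's exact test for yes/no and unordered outcomes.

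A trend test or proportional-odds model would also use the order. What matters is that one method is fixed before the data are seen.

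The cost is about one extra analysis sentence plus the scale definitions. It needs no more patients and, for symptoms, no more data. For X-ray, the sponsor should also confirm where the image and its reading enter the assessment schedule, since the current lists do not show them.

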- Viral load one day and one week after the last session
- Chest Xray changes one day and one week after the last session
- Percentage of patients with positive IgG serology one day and one week after the last session
- Percentage of patients with positive IgM serology one day and one week after the last session
- Pulmonary function test one day and one week after the last session
- Time to symptoms recovery
- Percentage of patients who required invasive intubation
- Time to recovery (negative PCR twice) – TTCR
- Mortality rate in 30 days
- Safety – percentage of adverse events

STUDY DESIGN

Subjects: Patients at Maimonides Medical Center (MMC)

Eligibility Criteria:

Patients who are (1) within 7 days of need of oxygen supply, (2) positive to SARS-CoV-2 through RT-PCR, (3) have at least one risk factor for bad prognosis of COVID-19: hypertension, diabetes mellitus, ischemic heart disease, smoking, age>50, etc., (4) have respiratory insufficiency: Room Air SpO₂ <94% or PaO₂/FiO₂<300mmHg, (5) are older than 18 years of age and (6) have ability to sign an informed consent will be included in the study.

Patients who are (1) negative to SARS-CoV-2 through RT-PCR, (2) have a HBOT contraindication: pneumothorax, pneumomediastinum, claustrophobia, ear/sinus disease which aren't allowed in HBOT, known chronic pulmonary disease: severe emphysema or known pulmonary bullae, (3) have pregnancy and/or (4) have inability to sign an informed consent will be excluded from study.

Design:

This study is a prospective randomized controlled, double blind clinical trial performed on laboratory confirmed COVID-19 infection admitted patients in MMC. It involves the use of MMC monoplace HBO chambers. The trial will include 30 patients who will undergo either hyperbaric oxygen therapy (HBOT) or Normobaric oxygen therapy (NBOT), randomized on a 2:1 ratio, within 4 days in addition to the standard treatment including oxygen, drugs, steroids, bronchodilators, antibiotics and others.

The evaluation procedure includes symptom monitoring, room air saturation, vital signs monitoring, pulmonary function and blood tests at baseline, one day and one week after the last session. In addition, one hour prior to and post session saturation and vitals will be monitored.

Data Collection Procedures:

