Upon signing an informed consent, the patients will be randomized 2:1 to hyperbaric oxygen therapy group (HBOT) and normobaric oxygen therapy group (NBOT) (Randomization will be performed using a computer software based on patient id). Following the randomization, the patients will undergo evaluation including symptoms, vitals, pulmonary function, blood tests.

The patients will undergo 8 sessions of either hyperbaric/normobaric oxygen therapy, 2 sessions per day, in 4 consecutive days. During the sessions, the symptoms and vitals will be monitored. 1 day and 1 week following the last session, reevaluation will be performed.

Protocol Day 1

1. Baseline evaluation: blood test including: arterial blood gases, 2 CBC tubes, 2 Gel tubes (10-15 cc total), vitals (temperature, blood pressure, heart rate, room air saturation), symptoms questionnaire, pulmonary function test.
2. Vitals (temperature, blood pressure, heartrate, room air saturation) one hour prior to session
3. One-hour session NBO/HBO
4. Vitals (temperature, blood pressure, heartrate, room air saturation) one hour after the session.
5. Vitals (temperature, blood pressure, heartrate, room air saturation) one hour before the 2nd session.
6. One-hour session NBO/HBO (8 hours following the first session)
7. Vitals (temperature, blood pressure, heartrate, room air saturation) one hour after the session.
8. Daily oxygen supply dose monitoring.

Protocol Day 2-4

1. Daily symptoms questionnaire
2. Vitals (temperature, blood pressure, heartrate, room air saturation) one hour prior to session
One-hour session NBO/HBO
3. Vitals (temperature, blood pressure, heartrate, room air saturation) one hour after the session.
4. Vitals (temperature, blood pressure, heartrate, room air saturation) one hour before the 2nd session.
5. One-hour session NBO/HBO (8 hours following the first session)
6. Vitals (temperature, blood pressure, heartrate, room air saturation) one hour after the session.
7. Daily oxygen supply dose monitoring.

Follow up Protocol

1. Repeat evaluations one day after the last session and one week after the last session:
 - Blood test including: arterial blood gases, 2 CBC tubes, 2 Gel tubes (10-15 cc total)
 - Vitals (temperature, blood pressure, heart rate, room air saturation)
 - Symptoms questionnaire
 - Pulmonary function test.
2. Oropharyngeal swab for SARS-CoV-2 RT-PCR every 3 days for 1 week
3. Clinical monitoring for 30 days

Data Analysis:

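### IgG and IgM outcomes count patients who were antibody positive before treatment; testing the Day 1 gel tube would allow seroconversion to be reported

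*Combined protocol and SAP*

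**What the plan says.** **Serology.** Study Objectives and Expected Outcomes both list as secondary outcomes "Percentage of patients with positive IgG serology one day and one week after the last session" and "Percentage of patients with positive IgM serology one day and one week after the last session". Neither mentions status before treatment. Data Analysis compares categorical variables by chi-square, also names Fisher's exact test, and describes neither a baseline adjustment nor a definition of seroconversion.

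**Blood samples.** The Design section places "pulmonary function and blood tests at baseline, one day and one week after the last session". Protocol Day 1, item 1, specifies "Baseline evaluation: blood test including: arterial blood gases, 2 CBC tubes, 2 Gel tubes (10-15 cc total", ahead of the first session. Follow up Protocol, item 1, repeats the same tubes one day and one week after the last session. No assay on the gel tubes is named at any visit.

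**Virology.** A further secondary outcome is "Viral load one day and one week after the last session". The only scheduled swabs are in Follow up Protocol, item 2: "Oropharyngeal swab for SARS-CoV-2 RT-PCR every 3 days for 1 week". No start day is given. The Day 1 list contains no swab. Eligibility requires a positive RT-PCR, without a date window or a quantitative result. Data Analysis plans t-tests both between and within the groups.

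**The concern.** Eligible patients may be up to 7 days past their first need for oxygen, so some could have IgG or IgM before the first session. Those patients cannot show a treatment effect on antibody development, yet they enter the numerator and denominator of both arms. Two things follow. Any real difference in seroconversion is diluted. And with only 20 and 10 patients, a chance difference in pre-treatment antibody status carries into the reported percentages, where it cannot be recognised unless baseline status is known.

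For viral load, a swab interval with no anchor leaves open whether samples fall at the two stated times. The planned within-group test also needs a pre-treatment value, and the plan does not schedule one.

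**Working it through.** **The plan's own figure.** The documents give no calculation for serology or viral load. The only calculated figure is the PaO₂/FiO₂ sample size of 7 and 13. With a difference of 30, the exact t-test power at 7 and 13 is 98.1% at SD 15, 95.6% at SD 16.5 and 91.9% at SD 18, so the figure reproduces at a mid-range SD. This point does not depend on it.

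**Inputs.** From the Sample Size section: 20 HBOT and 10 NBOT patients. Assumed, because the documents give no rates: baseline positivity b from 0 to 80%, and seroconversion among baseline negatives of c₁ = 70% in one arm (n = 20) and c₀ = 20% in the other (n = 10). These rates only illustrate the mechanism. Patients positive at baseline are taken to stay positive.

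**Dilution.** Positivity in an arm is b + (1 − b)c, so the arm difference is (1 − b)(c₁ − c₀). At b = 40%: 0.40 + 0.60 × 0.70 = 82% versus 0.40 + 0.60 × 0.20 = 52%, a difference of 30 points instead of 50. Power is for a two-sided Fisher test at 5%. In the last column it is averaged over the random number of baseline negatives.

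| b | Difference in positivity | Power, all patients | Expected baseline negatives (20 / 10 arm) | Power, baseline negatives |
|---|---|---|---|---|
| 0% | 50 points | 66% | 20 / 10 | 66% |
| 20% | 40 points | 50% | 16 / 8 | 57% |
| 40% | 30 points | 35% | 12 / 6 | 42% |
| 60% | 20 points | 21% | 8 / 4 | 21% |
| 80% | 10 points | 9% | 4 / 2 | 4% |

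**Chance imbalance at baseline.** The SD of the baseline difference is √[b(1 − b)(1/20 + 1/10)]. At b = 20% this is √(0.16 × 0.15) = 15.5 points, and at b = 50% it is √(0.25 × 0.15) = 19.4 points. The exact binomial probability of a gap of at least 20 points is 25.7%, 32.6%, 35.9% and 36.9% at b = 20, 30, 40 and 50%. For a gap strictly above 20 points it is about 14 to 25%.

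**Swab calendar.** Take the last session as day 0, with viral load due on days 1 and 7 and swabs every 3 days up to day 7:
- start on day 0: days 0, 3, 6 (neither target)
- start on day 1: days 1, 4, 7 (both targets)
- start on day 2: days 2, 5 (neither)
- start on day 3: days 3, 6 (neither)

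The line stands in the Follow up Protocol, directly after the item that sets visits at one day and one week. A start at the one-day visit is the natural reading, and it meets both targets.

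**Pre/post test of viral load.** The Day 1 list has no swab, and the entry RT-PCR is required only to be positive. The within-group test therefore has no scheduled first value.

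**The case against.** Point positivity compared between randomised arms is a legitimate estimand, and a baseline assay alone would not change what is counted. That stands: the gain comes only from redefining the outcome, and it is modest, absent at 60% baseline positivity and reversed at 80%.

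Three stronger readings are tempting, and the documents do not support them.

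- *Serology has no baseline sample.* The Design section schedules blood tests at baseline, and Day 1 draws the same gel tubes as follow-up. No assay is named for those tubes at any visit, so silence about IgG and IgM on Day 1 does not show that they will not be run.
- *The comparison is biased, or has a false-positive rate of 26 to 37%.* Those percentages are the chance of a baseline gap of at least 20 points. With identical true rates of 20 to 50% in both arms, Fisher's test rejects in only about 2 to 3% of trials.
- *Viral load will miss its time points.* Three of four listed starts do miss both on exact-day matching, but this counts possibilities and is not a risk. With a tolerance of one day either way (an assumption; no window is stated), none of the four misses both.

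The Adverse Event Reporting section also refers the reader to the research protocol of an overall study, which is not available here and might hold the laboratory list or swab days. That limits confidence about what is absent. These are, moreover, secondary outcomes that do not drive the sample size.

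**Conclusion.** The point holds as an inexpensive improvement to two secondary outcomes. As defined, IgG and IgM positivity mixes antibody status before treatment with seroconversion afterwards. The arm difference is diluted by the factor (1 − b), and the small arms add chance imbalance with an SD of about 15 to 19 points if 20 to 50% are positive at baseline. Neither arm is favoured systematically. Restricting to baseline negatives raises illustrative power from 50% to 57% at b = 20% and from 35% to 42% at b = 40%. All of these sizes rest on assumed baseline and conversion rates.

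The missing swab start day is a matter of missing detail. The absence of a scheduled pre-treatment viral load is a real gap, but a narrow one: it rules out the within-group pre/post test as written and leaves the between-arm comparison possible.

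**What to change.** 1. **Serology.** State that IgG and IgM are run on the Day 1 gel tube drawn before the first session. Make seroconversion among baseline negatives, at one day and one week after the last session, the outcome for each antibody, and report overall positivity descriptively. Restricting on a pre-treatment result keeps the randomised comparison. Cost: IgG and IgM testing of one stored sample per patient (30 samples) with no new blood draw, and a smaller denominator. If most patients prove positive at baseline, the restricted comparison will be too small to be informative, and the report should say so.
2. **Swabs.** State that they fall on days 1, 4 and 7 after the last session. This keeps the existing interval and costs nothing.
3. **Viral load.** Either use a quantitative result from the entry RT-PCR as the pre-treatment value, where one exists and its date is recorded, or limit the analysis of viral load to the between-arm comparison and drop the within-group test. Neither option needs a new procedure.

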The use of hyperbaric oxygen therapy (HBOT) includes breathing 100% oxygen in pressures higher than 1 absolute atmospheres (ATA), increasing the amount of oxygen dissolved in the plasma and the different tissues. During the session, oxygen partial pressure can increase from 100mmHg to 1700-2500mmHg (according to the applied pressure) [9]. In the last month, Chen et al. reported a case series of 5 severe COVID-19 patients treated with 3-8 HBOT sessions in addition to the standard therapy]10[. In all cases, they reported an increase in oxygen saturation, arterial oxygen content, lactate levels reduction, fibrinogen levels decrease and increase in lymphocytes number. In addition, the patients' chest CT showed improved signs. Symptomatic relief started following the 2nd session. No significant adverse events were reported [9].

These findings may be explained by the known physiological effects of HBOT, related to the SARS-CoV-2 virus pathogenesis:

- **Increased competitive binding of oxygen to the hemoglobin molecule**
 - it has been postulated recently the SARS-CoV-2 bind to the heme component in the hemoglobin molecule and reduces the oxygen affinity to hemoglobin. During HBOT, the increased amount of available oxygen molecules increases the binding to the hemoglobin molecules. This has shown significant beneficial effects in cases of another competitive molecule such as carbon monoxide intoxication, where HBOT induces carbon monoxide unbinding and release of the red blood cells [12, 11]. If the virus indeed affects the Heme component (as suggested above) in a competitive affinity, HBOT may significantly improve and normalize the red blood cells oxygen carrying capability.
- **Tissue oxygenation** – The oxygen content in the different tissues is multiplied by 25-30 times [13]. This effect has two therapeutic aspects: First, overcoming pulmonary hypoxia (either shunt or VQ mismatch) by increasing the FiO₂ significantly. By increasing the pulmonary oxygen gradient, oxygen diffusion increases and can overcome the inflammation in the alveoli and the thickened fibrosis caused by ARDS. These effects have been demonstrated in patients who developed ARDS after suffering a blunt chest trauma who were treated with HBOT. In these patients, HBOT induced improvement and rapid normalization of PaO₂, PaO₂/FiO₂ in addition to cardiac parameters CI and SVI]14[. Second, during HBOT, the amount of oxygen dissolved in the plasma

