- Mortality rate in 30 days
- Safety – percentage of adverse events

Timetable: 12 months

Adverse Event Reporting

Subjects will be monitored for adverse events (AEs) during the entire study and more particularly, during and after each treatment session by clinical inquiry, clinical observation and (when applicable) by clinical examination. AE information will be documented and all subjects will be questioned about AEs at each visit during the treatment period and at the follow-up visits. AEs will also be recorded whenever spontaneously reported by the subject. Event description, date of onset, intensity,

duration, treatment for AE, whether the AE was resolved and probable relationship to the study product will be recorded onto case report forms (CRFs).

The investigator must record all serious adverse events regardless of treatment or relationship to investigational product as soon as s/he is informed of the event.

Any serious adverse event (SAE) which occurs after a patient has entered the study (after signing informed consent), must be reported. The original copy of the serious adverse event form must be kept with the documentation at the site.

Patients who have had an SAE during the treatment period must be followed clinically until all parameters (including laboratory), have either returned to normal, have stabilized or are otherwise explained.

SAEs should be reported by the investigator to competent authorities and ethics committees according to local requirements.

For more information, see research protocol from overall study.

REFERENCES

1. Goh, K.J., et al., *Rapid Progression to Acute Respiratory Distress Syndrome: Review of Current Understanding of Critical Illness from COVID-19 Infection*. Ann Acad Med Singapore, 2020. **49**(3): p. 1-9.
2. Mehta, P., et al., *COVID-19: consider cytokine storm syndromes and immunosuppression*. Lancet, 2020. **395**(10229): p. 1033-1034.
3. Ruan, Q., et al., *Clinical predictors of mortality due to COVID-19 based on an analysis of data of 150 patients from Wuhan, China*. Intensive Care Med, 2020.
4. Zhu, N., et al., *A Novel Coronavirus from Patients with Pneumonia in China, 2019*. N Engl J Med, 2020. **382**(8): p. 727-733.
5. Wu, F., et al., *A new coronavirus associated with human respiratory disease in China*. Nature, 2020. **579**(7798): p. 265-269.
6. Liu, W. and H. Li, *COVID-19: Attacks the 1-Beta Chain of Hemoglobin and Captures the Porphyrin to Inhibit Human Heme Metabolism*. 2020.

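### The only formal between-arm criterion for adverse events and 30-day mortality is p<0.05, with no interval for the excess risk; with 20 v 10 patients a true 20-point excess would reach it in at most about one trial in five

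*Combined protocol and SAP*

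**What the plan says.** Safety appears as one secondary line, "Safety – percentage of adverse events", in both Study Objectives and Expected Outcomes, next to 30-day mortality. Neither place says whether the percentage counts patients or events, and neither gives an expected rate.

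No analysis is written for safety in particular, so the general rules in Data Analysis apply: "Categorical data will be expressed in numbers and percentages and compared by chi-square tests". A further sentence allows an exact test: "Univariate analyses were performed using Chi-Square/Fisher's exact test to identify significant variables". The criterion is "A value of $p<0.05$ will be considered significant". The document specifies no confidence interval, risk difference, safety threshold or rule for reading a non-significant comparison.

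The Sample Size section rests on PaO2/FiO2 alone and plans 20 HBOT and 10 NBOT patients. Adverse Event Reporting has each event recorded with its intensity, duration, outcome and relationship to treatment, and requires serious adverse events to be reported to authorities and ethics committees. It ends by pointing to the protocol of an overall study.

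**The concern.** A significance test asks whether excess harm has been shown. When it is non-significant in 30 patients, it does not tell the reader how much harm remains possible. That needs an interval for the difference, and none is planned. Followed as written, the between-arm safety result would often be a p-value above 0.05 with no statement of the excess risk that the trial failed to exclude.

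The background shows how easily such a result can be taken as reassurance. A case series of 5 patients without significant adverse events is carried forward in Background and Significance as safety evidence. At stake is whether readers of this trial can tell absence of evidence of harm from evidence that harm is small.

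**Working it through.** **Inputs.** From the document: 20 HBOT and 10 NBOT patients, 15% dropout, chi-square or Fisher, p<0.05. Two-sided testing is stated for the t-tests and assumed here for the categorical tests. Chi-square is taken without continuity correction. True event rates are assumptions, because the document gives none. The unit is taken as patients with at least one event.

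**The plan's own figure.** The document states no power or precision for safety. Its one power statement, 7 NBOT and 13 HBOT for a PaO2/FiO2 difference of 30 with 95% power, does reproduce. With SDs of 15 and 18 the common SD is √[(15² + 18²)/2] = √274.5 = 16.6, and a two-sample t-test has 95.4% power. That figure carries nothing over to adverse events.

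**Step 1: what must be observed.** For a of 20 HBOT and b of 10 NBOT patients with an event,

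χ² = 30 × [a(10 − b) − b(20 − a)]² / [20 × 10 × (a + b) × (30 − a − b)].

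- 6/20 v 0/10: χ² = 30 × 60² / (200 × 6 × 24) = 3.75, p = 0.053, not significant.
- 7/20 v 0/10: χ² = 30 × 70² / (200 × 7 × 23) = 4.57, p = 0.033, significant.

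| NBOT events | Smallest HBOT count with p<0.05, chi-square | Fisher |
|---|---|---|
| 0/10 | 7/20 | 8/20 |
| 1/10 | 10/20 | 10/20 |
| 2/10 | 12/20 | 14/20 |

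**Step 2: how often harm is flagged.** Power is the sum of Bin(a; 20, p_H) × Bin(b; 10, p_N) over all tables with a/20 > b/10 and p<0.05.

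True excess of 20 percentage points:

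| NBOT v HBOT | Chi-square | Fisher |
|---|---|---|
| 10% v 30% | 15.6% | 9.8% |
| 20% v 40% | 16.5% | 13.1% |
| 30% v 50% | 17.3% | 11.6% |
| 40% v 60% | 18.3% | 11.2% |
| 50% v 70% | 19.8% | 14.5% |

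True tripling:

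| NBOT v HBOT | Chi-square | Fisher |
|---|---|---|
| 5% v 15% | 1.3% | 0.4% |
| 10% v 30% | 15.6% | 9.8% |
| 15% v 45% | 35.2% | 29.6% |
| 20% v 60% | 57.6% | 44.5% |
| 25% v 75% | 78.4% | 68.5% |
| 30% v 90% | 94.5% | 92.3% |

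A tripling is flagged half the time at an NBOT rate of about 18.5% by chi-square and about 22% by Fisher. With 15% dropout (17 v 8), power at 10% v 30% falls to 10.2% (Fisher 5.0%).

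**Step 3: what an interval would show.** Take an observed 6/20 v 1/10.

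- χ² = 30 × (54 − 14)² / (200 × 7 × 23) = 1.49, so p = 0.22. Fisher gives 0.37.
- The Wilson 95% limits are 0.145 to 0.519 for HBOT and 0.018 to 0.404 for NBOT.
- Newcombe lower limit: 0.20 − √[(0.30 − 0.145)² + (0.404 − 0.10)²] = −0.14.
- Newcombe upper limit: 0.20 + √[(0.519 − 0.30)² + (0.10 − 0.018)²] = +0.43.

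The planned test reports no significant difference. The interval reports +20 points and does not exclude an excess of 43.

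For zero events in 20 HBOT patients, the upper limit of the exact two-sided 95% interval is 1 − 0.025^(1/20) = 16.8%.

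**The case against.** A reader might infer three stronger things that the documents do not support.

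1. That a tripled adverse-event rate would usually be missed whatever the background rate. The outcome appears to cover all adverse events, in inpatients with respiratory insufficiency who are questioned at each visit and monitored for 30 days, so a high NBOT rate is plausible. Above about 22% a tripling is found more often than missed by either test, and at 30% v 90% it is found over 90% of the time. The tripling statement therefore needs its condition on the control rate.
2. That safety is judged only by a p-value. Counts and percentages per arm are already planned, events are recorded individually with intensity and relationship, and serious events are reported. What is true is narrower: the test is the only formal between-arm criterion.
3. That the trial will read non-significance as safety. No sentence says so. The use made of the 5-patient series shows a risk of that reading, not a rule.

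It can also be said that the trial was sized for oxygenation, that an interval adds no information beyond the counts, that readers could compute one themselves, and that the overall study's protocol may hold a fuller safety plan. The last point stands: what is said here is missing is missing from this document. The others do not remove the point. A small sample is a reason to state the uncertainty in the report instead of leaving readers to work it out.

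**Conclusion.** The point holds in a limited form. This document's sole formal between-arm criterion for adverse events and 30-day mortality is a test at p<0.05, with no interval for the excess risk. Over assumed NBOT rates of 10% to 50%, a true 20-point excess (one additional affected patient for every five treated) goes unflagged in at least 80% of trials. That conclusion does not depend on events being rare. The statement about a tripling does: it is usually missed at an NBOT rate of about 15% or lower, which is where 30-day mortality and serious events would fall if they prove infrequent.

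The figures rest on full recruitment of 20 and 10, two-sided tests, patients as the unit, and assumed rates. This is a cheap improvement to the analysis and reporting. It does not show that the trial is unsafe or that its authors will claim safety.

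**What to change.** For adverse events, serious adverse events and 30-day mortality:

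- Keep the planned number and percentage per arm, defined as patients with at least one event, and add an exact 95% confidence interval for each arm.
- Replace the p<0.05 decision by the HBOT minus NBOT risk difference with a 95% confidence interval (score/Newcombe or exact), and name the method in advance.
- State that a non-significant difference will not be reported as evidence of safety.
- State that zero events in 20 HBOT patients will be reported with its upper limit of 16.8%.

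The cost is a few sentences in Data Analysis and a few extra table columns. It needs no more patients, data or procedures and leaves clinical management unchanged. The safety statement will read less favourably, but it will show what the trial can and cannot exclude.
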